6.4 ASSESSMENT TIME WINDOWING

No analysis visit windows will be utilized in this study and all safety and effectiveness assessment summaries will be based on the nominal protocol-specified assessment times.

6.5 POOLING OF INVESTIGATOR SITES

Data from all four sites will be pooled together for reporting in total.

6.6 ADJUSTMENTS FOR MULTIPLICITY

No adjustments for multiplicity will be performed as no formal hypothesis testing is planned.

6.7 EXAMINATION OF SUBGROUPS

Subgroup analyses will consist of gender identity (cisgender, transgender male, transgender female, gender fluid, other), age group (18-24, 25-34, 35-44, 45-50), and the Cellulite Dimple – At Rest Scale as assessed during the Screening visit (Both Sides Grade 2, Both Sides Grade 3, Side with Different Grades) for the primary effectiveness endpoint. Only descriptive statistics will be provided for subgroup analysis.

7 PARTICIPANT SUMMARIES

7.1 ANALYSIS POPULATIONS

7.1.1 Enrolled

The Enrolled population consists of all participants who signed the informed consent form (ICF).

7.1.2 Safety

The Safety population consists of all Enrolled participants who received at least one Resonic treatment session (started or completed).

7.1.3 Evaluable

The Evaluable population consists of participants in the Safety population who completed the Resonic treatment plan (completed two treatment sessions) bilaterally for at least one location.

7.2 PARTICIPANT DISPOSITION

The following will be summarized overall using the Enrolled population. Denominators for percentages will be the number of participants who receive a Resonic treatment session/Safety population:

- The number of participants enrolled (Enrolled population)
- The number of participants who received at least one Resonic treatment session (Safety population)
- The number and percentage of participants who completed the Resonic treatment plan bilaterally for at least one location (Evaluable population)
- The number and percentage of participants who completed the 12 weeks evaluation period after last treatment.
- The number and percentage of participants who completed the study
- The number and percentage of participants who withdrew early and reason for withdrawal

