All eligible participants must sign the informed consent form prior to enrollment in the study. The participant and the Investigator or designee will discuss the benefits and risks of the study and review the participant consent form to ensure the participant understands the scope of the study. It is the Investigator's or designee's responsibility to ensure that participants understand that participation in the study is voluntary, and that the quality of their medical care will not be adversely affected if they decline to participate in the study. Adequate time for any questions and explanations will be provided. Participants will have the opportunity to discuss the study with their surrogates and have time to think about it prior to participating. Participants may withdraw their consent at any time throughout the course of treatment. Once the participant understands the informed consent, he/she will be allowed to voluntarily agree to participate by signing the document. The investigator/designee is responsible for obtaining informed consent prior to enrollment in the study and ensuring that the participant has a copy of the document for their records. The participant is considered enrolled in the study after the informed consent has been signed and it has been verified that the participant meets all inclusion criteria and none of the exclusion criteria.

RECORDS MANAGEMENT

Study Records Retention: Each site will maintain appropriate medical records for this study in accordance with institutional requirements including, but not limited to, hospital records, laboratory tests, pharmacy dispensing records, x-rays, and clinical charts. As part of study participation, each site will permit the Sponsor ZELTIQ Aesthetics, Inc., or its designee, to examine (and when required by applicable law, to copy) clinical records for the purposes of quality assurance reviews, audits and evaluation of study safety and progress.

- i. Essential documents, as listed below, must be retained by the site until at least 2 years after completion or termination of the investigation, or longer if:

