4 DETERMINATION OF SAMPLE SIZE

Up to sixty participants will be enrolled and treated in this study. The sample size is based on clinical and practical exploratory considerations and not on a formal statistical power calculation.

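### SAP 7.2 lets the early-withdrawal numerator include untreated participants while the denominator is treated participants only, so the percentage can be overstated

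*SAP*

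**What the plan says.** SAP 7.2 names the set to be summarised: "The following will be summarized overall using the Enrolled population". It then sets the base for every percentage in the table: "Denominators for percentages will be the number of participants who receive a Resonic treatment session/Safety population". The last row of the list is "The number and percentage of participants who withdrew early and reason for withdrawal", with no limit to treated participants. The table list in SAP 15.1 also labels Table 14.1.1 as Enrolled.

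The sets are defined as follows.

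- SAP 7.1.1: "The Enrolled population consists of all participants who signed the informed consent form (ICF"
- SAP 7.1.2: "The Safety population consists of all Enrolled participants who received at least one Resonic treatment session (started or completed"
- SAP 7.1.3: "The Evaluable population consists of participants in the Safety population who completed the Resonic treatment plan", that is, both sessions, bilaterally, for at least one location.

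The protocol uses a narrower meaning of enrolment. Under Study Participant Informed Consent, a participant is "considered enrolled in the study after the informed consent has been signed and it has been verified" that all inclusion criteria and no exclusion criteria are met. The protocol's Study Design section and SAP section 3 both state the same rule of consent plus eligibility.

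**The concern.** A percentage describes a population only if everyone counted in its numerator also belongs to its denominator. For the early-withdrawal row, the SAP draws the numerator from all who consented and the denominator from those treated. The protocol allows withdrawal at any time, and consent comes before treatment, so a participant can leave between signing and the first session. A programmer who follows SAP 7.2 literally would count that exit over a base that excludes the person.

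The row matters because the study has a single arm, the primary analysis is confined to the Evaluable population and to analyzable images, and SAP 6.3 rules out imputation. Readers will use the disposition table to see who is missing from the effectiveness result. A withdrawal percentage that mixes exits before treatment with losses after treatment does not show this clearly.

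**Working it through.** **Plan's own figure.** There is none to reproduce. The documents give no withdrawal percentage, dropout rate, screen-failure count or number of untreated participants.

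**Which rows are exposed.** The rows of SAP 7.2 that carry a percentage are:

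- *Evaluable:* nested in Safety by definition (SAP 7.1.3), so coherent.
- *Completed the 12-week evaluation:* timed from the last treatment, so it presupposes treatment and is coherent.
- *Completed the study:* normally presupposes treatment, so normally coherent.
- *Withdrew early, with reason:* not restricted to treated participants, so exposed.

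The Enrolled and Safety rows are counts without percentages.

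**Notation.** T is the number treated (Safety), w the number treated who withdrew early, and u the number who consented, were never treated and are counted as withdrawn.

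- Literal SAP 7.2: (w + u)/T
- Treated participants only: w/T
- All treated plus untreated withdrawals as the base: (w + u)/(T + u)
- Overstatement of the literal rule against w/T: (w + u)/T − w/T = u/T

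**Inputs.** T = 60 is the planned maximum in SAP section 4 ("Up to sixty participants will be enrolled and treated in this study"). The values of w and u are assumptions, shown over a range. With w = 3:

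| u | Literal (3+u)/60 | Treated only 3/60 | Base T+u: (3+u)/(60+u) |
|---|---|---|---|
| 0 | 5.0% | 5.0% | 5.0% |
| 3 | 10.0% | 5.0% | 9.5% |
| 6 | 15.0% | 5.0% | 13.6% |
| 12 | 25.0% | 5.0% | 20.8% |
| 20 | 38.3% | 5.0% | 28.8% |

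Each 3 untreated people counted as withdrawn add 3/60 = 5 points. With T = 50 they add 3/50 = 6 points.

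**Consistency check.** If every other treated participant completes, the completed and withdrawn percentages sum to (T − w)/T + (w + u)/T = 1 + u/T. At T = 60 this is 105% for u = 3 and 120% for u = 12. A table with such a total visibly mixes two populations.

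**Role of the two enrolment definitions.** The denominator is Safety under either definition. An eligible participant who leaves before the first session satisfies both the SAP 7.1.1 rule and the protocol rule, so the mismatch can arise under either. The consent-only definition also admits screen failures to the summarised set. This enlarges the possible u but is not the source of the problem.

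**The case against.** The strongest reply is that this is loose wording rather than an error. SAP 7.2 declares its treated denominator openly. The percentages begin only after the treated row, and the other percentage rows all sit within, or normally within, the Safety population. On that layout the natural reading is that withdrawals are counted among treated participants too. No text says that screen failures or untreated consenters are recorded as early withdrawals. The protocol assigns participant numbers to those who meet all criteria, which makes screen failures an unlikely route. Much of the protocol text around visits is redacted, so how pre-treatment exits are recorded cannot be checked. The Evaluable and 12-week percentages speak more directly to attrition for the primary endpoint, and Listing 16.2.1 should allow treated withdrawals to be recovered.

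Most of this stands, and it limits the point. It does not remove it: SAP 7.2 expressly names Enrolled as the set summarised, and nothing tells the programmer to restrict the last row.

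Three stronger readings may tempt a reader, and the documents support none of them.

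- *The withdrawal percentage is wrong.* No percentage is reported, and the figure is wrong only if u is above zero.
- *The conflict over Enrolled produces the error.* It does not, because the mismatch can arise under either definition.
- *The cap of sixty changes meaning between the documents.* SAP section 4 speaks of participants enrolled and treated, and SAP section 3 uses the protocol's rule. An analysis-set label in 7.1.1 does not redefine the recruitment limit.

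**Conclusion.** The point holds in a limited form. SAP 7.2, followed literally, allows a numerator from one set over a denominator from another in the early-withdrawal and withdrawal-reason rows. The overstatement is u/T: zero if no untreated participant is counted as withdrawn, and 5 points per 3 such people if T = 60. The size in practice is unknown, because u and w are not given anywhere and the values used here are illustrative.

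The inconsistency between SAP 7.1.1 and both the protocol and SAP section 3 is a real but separate defect. It also bears on the protocol-deviation summary, which SAP 7.4 places on the Enrolled population.

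The consequence is confined to descriptive disposition reporting. Effectiveness is summarised on Evaluable, adverse events on Safety, and SAP 6.2 plans no hypothesis test, so no effectiveness or safety estimate changes.

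**What to change.** 1. In SAP 7.2, state that the early-withdrawal and withdrawal-reason rows count only Safety participants whenever the denominator is Safety.
2. Show screen failures and exits after consent but before the first session as separate counts, without a percentage.
3. Keep the consent-based set of SAP 7.1.1 but rename it Consented, so that it no longer conflicts with the enrolment rule in the protocol and SAP section 3. Carry the new name through SAP 7.2, 7.4 and the table list.
4. Redefine Safety in SAP 7.1.2 as all consented participants who started or completed at least one session.

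Rewriting 7.1.1 to require verified eligibility looks simpler but carries a risk. Safety is defined as a subset of Enrolled, and deviations are summarised on Enrolled. A participant who was treated and later found ineligible could then arguably drop out of both the safety tables and the deviation summary. Renaming the set avoids that loss.

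The cost is a few sentences in the SAP and one revised table shell. No new data are needed.

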7.3 DEMOGRAPHIC AND BASELINE CHARACTERISTICS

7.3.1 Demographic and Baseline Characteristics

Demographic variables will include age, age group (18-24, 25-34, 35-44, 45-50), sex (reported at birth), gender identity, race, and ethnicity. Baseline characteristics include height (cm), weight (kg), BMI, Fitzpatrick Skin Type, and Cellulite Dimple – At Rest Scale (Grade 2, Grade 3 by left and right side and collectively). Demographics and baseline characteristics will be presented in a by-participant listing and summarized descriptively for the Safety population.

7.3.2 Medical History

Medical history, as collected at screening, will be coded using the Medical Dictionary for Regulatory Activities (MedDRA) version 26.0 to determine system organ class (SOC) and preferred term (PT). Medical histories will be summarized descriptively in descending order of frequency for the Safety population and presented in a by-participant listing.

7.3.3 Medications

The number and percentage of participants taking medications will be summarized by generic drug name based on ATC drug class 3 for the Safety population. If ATC drug class 3 is not available, the highest-level ATC classification available will be used. Medications will be displayed in descending order of frequency of ATC Class and then descending order of frequency of preferred term within each ATC Class. Medications will be coded using World Health Organization Drug Dictionary Anatomical Therapeutic Chemical (WHO/ATC) classification index version Global B3/C3-format March 1, 2023.

All medications captured on CRFs will appear in by-participant data listings.

7.4 PROTOCOL DEVIATIONS

Protocol deviations will be captured on CRFs and categorized and summarized by type using the Enrolled population. CSR reportable protocol deviations will be summarized for the Enrolled population. CSR reportable status will be determined by AbbVie and then transferred to ARA in a programmable format, such as Excel.

8 MEASUREMENTS OF TREATMENT EXPOSURE AND COMPLIANCE

Counts and percentages of participants that completed only one or both treatments will be provided in the participant disposition summary table. Descriptive statistics summarizing the duration of each treatment session, the number of dimples treated per session, the change in treatment duration and the change in the number of dimples treated for a given participant will be summarized. Treatment duration in minutes will be calculated as the sum of total doses per dimple per session as collected on the Site Treatment Data CRF form since each dose takes 1 min.

9 EFFECTIVENESS EVALUATION

9.1 EFFECTIVENESS ENDPOINT(S)

9.1.1 Primary Effectiveness Endpoint

Binary (yes/no) correct identification of baseline vs 12-week post-final treatment images of the treated body area(s) by at least two out of three blinded independent photo reviewers.

9.1.2 Secondary Effectiveness Endpoint

Improvement in the appearance of cellulite as determined by the study participants selecting “Agree” or “Strongly Agree” as answers to the Participant Satisfaction Survey question(s) “In comparison to the pre-treatment photo, the final photograph of the treatment area appears improved.” at the 12-week post-final treatment visit by side (participant’s left or right).

9.1.3 Exploratory Effectiveness Endpoints

- The number of participants who have improvement in the appearance of cellulite as determined by the study participants selecting “Agree” or “Strongly Agree” as answers to the Participant Satisfaction Survey question(s) “In comparison to the pre-treatment photo, the final photograph of the treatment area appears improved.” on one or two sides at the 4-week post-first treatment, 12, 26, and 52-week post-final treatment visit.
- Binary (yes/no) improvement in the appearance of cellulite as determined by the study participants selecting “Agree” or “Strongly Agree” as answers to the Participant Satisfaction Survey question(s) “In comparison to the pre-treatment photo, the final photograph of the treatment area appears improved.” at the 4-week post-first treatment, 26, and 52-week post-final treatment visits by side (participant’s left or right).
- Overall average pain per participant derived as the average of the responses to “The OVERALL pain score DURING the procedure?” and “The OVERALL pain score AFTER the procedure?” for all treatment sides on the Procedure Tolerability Questionnaire at each treatment visit.
- GAIS as determined by the investigator at the 4-week post-first treatment, 12, 26, and 52-week post-final treatment visits.
- Actual and change from baseline in Body Q™ Appraisal of Cellulite, Satisfaction with Buttocks, and Satisfaction with Hip & Outer Thigh Rausch transformed total scores at the baseline, 4-week post-first treatment, 12, 26, and 52-week post-final treatment visits.

9.2 EFFECTIVENESS ANALYSIS

9.2.1 Primary Effectiveness Analysis

The number and proportion of analyzable images that are correctly identified as baseline or 12-week post-final treatment by at least two out of three blinded IPRs will be summarized using the Evaluable population. The primary effectiveness objective will be met if $\geq 70\%$ of the baseline vs 12-week post-final treatment images of the treated body area(s) are correctly identified by at least two out of the three blinded IPRs.

9.2.2 Supportive Analysis of the Primary Effectiveness Endpoint

The primary effectiveness analysis will be repeated for subgroup analyses with gender, age, and the Cellulite Dimple – At Rest Scale as assessed at Screening using the Evaluable population.

9.2.3 Secondary Effectiveness Analysis

The number and proportion of analyzable images by side that participants indicate as improved in cellulite using the Participant Satisfaction Survey at the 12-week post-final treatment visit compared to baseline will be summarized using the Evaluable population.

9.2.4 Exploratory Effectiveness Analyses

All exploratory effectiveness analyses will be descriptive and summarized using the Evaluable population.

- Number and proportion of participants who have one or two sides improved at the 4-week post-first treatment, 12, 26, and 52-week post-final treatment visits via the Participant Satisfaction Survey.
- Number and proportion of sides that are improved at the 4-week post-first treatment, 26, and 52-week post-final treatment visits via the Participant Satisfaction Survey.
- Descriptive statistics for overall average pain per participant at the two treatment visits.
- Descriptive statistics for GAIS score at the 4-week post-first treatment, 12, 26, and 52-week post-final treatment visits via the investigator GAIS.
- Descriptive statistics for actual and change from baseline in Body Q™ Appraisal of Cellulite, Satisfaction with Buttocks, and Satisfaction with Hip & Outer Thigh Rausch transformed total scores at the 4-week post-first treatment, 12, 26, and 52-week post-final treatment visits.

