5.3 PROCEDURE TOLERABILITY QUESTIONNAIRE (ASSESSMENT 1 IN THE PROTOCOL)

The Procedure Tolerability Questionnaire is used to assess the comfort of the RAP treatment. It is divided into two sections (participant's right or left side) of three questions. The overall average pain per participant will be derived as the average of the responses to "The OVERALL pain score DURING the procedure?" and "The OVERALL pain score AFTER the procedure?" for all treatment sides. The overall average pain score cannot be computed if both questions are not answered. The individual responses are scored from 0 to 10, where higher scores indicated increased pain.

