15 TABLES OF CONTENTS FOR APPENDICES

15.1 TABLES

Table Number	Population	Title
14.1.1	Enrolled	Participant Disposition
14.1.2	Enrolled	CSR Reportable Protocol Deviations
14.1.3	Safety	Demographics and Baseline Characteristics
14.1.4	Safety	Medical History: Number of Participants with History
14.1.5	Safety	Medications: Number of Participants with Medications
14.1.6	Safety	Treatment Exposure
14.2.1.1	Evaluable	IPR of Study Images: Summary of Baseline vs. 12-Week Post-Final Treatment
14.2.1.2	Evaluable	IPR of Study Images: Summary of Baseline vs. 12-Week Post-Final Treatment by Subgroup
14.2.2.1	Evaluable	Summary of Improvement in Appearance of Cellulite via Participant Satisfaction Survey by Side and Visit
14.2.2.2	Evaluable	Summary of Number of Participants with Improvement in Appearance of Cellulite via Participant Satisfaction Survey on one side or two by Visit
14.2.3	Evaluable	Summary of Improvement in Appearance of Cellulite via Investigator GAIS by Visit
14.2.4	Evaluable	Summary of Overall Pain by Visit
14.2.5.1	Evaluable	Summary of Participant Body-Q Appraisal of Cellulite Rasch Transformed Total Score
14.2.5.2	Evaluable	Summary of Participant Body-Q Satisfaction with Buttocks Rasch Transformed Total Score
14.2.5.3	Evaluable	Summary of Participant Body-Q Satisfaction with Hip & Outer Thigh Rasch Transformed Total Score
14.3.1.1	Safety	Adverse Events: Overall Number (%) of Participants with Adverse Events
14.3.1.2	Safety	Adverse Events by System Organ Class and Preferred Term
14.3.1.3	Safety	Serious Adverse Events by System Organ Class and Preferred Term
14.3.1.4	Safety	Adverse Device Effects by System Organ Class and Preferred Term

14.3.1.5	Safety	Serious Adverse Device Effects by System Organ Class and Preferred Term
14.3.1.6	Safety	Unanticipated Adverse Events by System Organ Class and Preferred Term
14.3.1.7	Safety	Unanticipated Adverse Device Effects by System Organ Class and Preferred Term
14.3.2	Safety	Known Physiological Responses

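### Procedure pain on the 0-10 score is tabulated only in the Evaluable population, so the session 1 summary leaves out treated participants who did not go on to complete the treatment plan

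*SAP*

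**What the plan says.** SAP 5.3 gives the purpose of the instrument: "The Procedure Tolerability Questionnaire is used to assess the comfort of the RAP treatment". Responses run from 0 to 10, with higher meaning more pain. A participant's overall average is taken over the during-procedure and after-procedure items on all treated sides.

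SAP 9.1.3 makes this average an exploratory effectiveness endpoint, defined "for all treatment sides on the Procedure Tolerability Questionnaire at each treatment visit". SAP 9.2.4 then sets one population for the whole exploratory group: "All exploratory effectiveness analyses will be descriptive and summarized using the Evaluable population". The pain item in that list reads "Descriptive statistics for overall average pain per participant at the two treatment visits". The table list in SAP 15.1 agrees: Table 14.2.4, "Summary of Overall Pain by Visit", carries the label Evaluable.

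The two relevant populations are:

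- **Safety (SAP 7.1.2):** "all Enrolled participants who received at least one Resonic treatment session (started or completed").
- **Evaluable (SAP 7.1.3):** members of Safety who "completed the Resonic treatment plan (completed two treatment sessions) bilaterally for at least one location".

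**The concern.** A pain score given at the first treatment visit describes the procedure just delivered. Whether it enters the table depends on what happens afterwards, namely completion of a second session on both sides of at least one location. Pain at session 1 is a plausible reason not to return or not to finish, so the selection may be related to the quantity being summarised. The same rule drops the session 2 score of someone who started that session but did not complete it and is not Evaluable as a result.

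The other exploratory items measure cosmetic result or satisfaction with appearance, where restricting to participants who had the full regimen is defensible. Pain is the one item in the list that records what the treatment felt like. For comparable outputs (exposure in Table 14.1.6, adverse events, and known physiological responses in Table 14.3.2) the SAP already uses the Safety population. As planned, session 1 duration and number of dimples treated are reported for everyone treated, but session 1 pain only for those who completed the plan. A reader could take the tabulated mean as the pain to expect at a first session when it describes a selected subset.

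**Working it through.** **Which outputs carry the score.** SAP 15.1 lists 23 tables. One reports the 0-10 score: Table 14.2.4, in the Evaluable population. None reports it in the Safety population. Other outputs touch on pain or on non-completion:

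| Output | Population or type | What it gives |
|---|---|---|
| Table 14.3.2 | Safety | Number and proportion with Pain/Discomfort as a response; no 0-10 intensity |
| Tables 14.3.1.1 to 14.3.1.7 | Safety | Adverse event incidence |
| Disposition (SAP 7.2 and 8) | Safety denominator | Percentage Evaluable, withdrawal reasons, number with one or both treatments |
| Listing 16.2.6.3 | Listing | Individual questionnaire data, not summarised |
| Listing 16.2.9.1 | Listing | Diary side effects, not summarised |

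**Size of the effect.** The plan states no figure to reproduce. Define:

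- N = treated participants with a session 1 score. The value 60 is used for illustration; SAP 4 allows up to 60.
- k = those of the N who are not Evaluable (assumed).
- m = session 1 mean in Evaluable participants, the value Table 14.2.4 would show.
- g = session 1 mean in the k others, minus m (assumed).

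All-treated mean = [(N − k)·m + k·(m + g)] / N = m + (k/N)·g.

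Shift = all-treated mean minus tabulated mean = (k/N)·g.

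| k of 60 | k/N | g = 1 | g = 2 | g = 4 | g = −2 |
|---|---|---|---|---|---|
| 0 | 0% | 0 | 0 | 0 | 0 |
| 3 | 5% | 0.05 | 0.10 | 0.20 | −0.10 |
| 6 | 10% | 0.10 | 0.20 | 0.40 | −0.20 |
| 12 | 20% | 0.20 | 0.40 | 0.80 | −0.40 |

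Direct check with an assumed Evaluable mean of 4:

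- k = 6, g = 2: (54×4 + 6×6)/60 = 4.2, shift 0.2.
- k = 6, g = 4: (54×4 + 6×8)/60 = 4.4, shift 0.4.
- k = 3, g = 4: (57×4 + 3×8)/60 = 4.2, shift 0.2.
- k = 6, g = −2: (54×4 + 6×2)/60 = 3.8, shift −0.2.

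The shift depends only on the share k/N and on g, so the same shares give the same results if fewer than 60 are enrolled.

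**The case against.** The strongest reply is that this is a choice of population and not an error. The SAP classes pain as exploratory effectiveness, applies one stated population to that whole group, and is consistent across 9.1.3, 9.2.4 and 15.1. A fixed completer set also keeps the two visit summaries on essentially the same people, which the change gives up. That is true, and it is the real cost of the change. It does not make the completer set suitable for describing session 1.

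Nor does pain in non-completers disappear from the report. Pain/Discomfort incidence and adverse events use the Safety population, and the protocol has each adverse event record its impact on study treatment. Disposition shows the share who are Evaluable, and SAP 8 adds: "Counts and percentages of participants that completed only one or both treatments will be provided in the participant disposition summary table". Listing 16.2.6.3 holds the individual scores. A careful reader could see how many were left out and look up their values. This stands and lowers the importance, but no planned output gives the all-treated summary.

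The exclusion may also be small. Someone who stops at one location but completes another bilaterally remains Evaluable. A participant who stopped during session 1 may lack the answers SAP 5.3 needs for a score, so the change may recover fewer people than the Safety and Evaluable counts suggest. The link between pain and non-completion is plausible but not documented. Finally, the protocol's endpoint and assessment text is largely redacted, so it cannot be said whether the classification began there or whether the choice was an oversight.

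**Conclusion.** The concern holds, as a minor point. The only planned summary of the 0-10 score conditions session 1 pain on later completion of the plan. Under the assumed 5% to 10% outside Evaluable and a gap of 1 to 4 points, the tabulated session 1 mean would be 0.05 to 0.4 points below the all-treated mean. At an assumed 20% and a 4-point gap it would be 0.8 points below. The difference vanishes if everyone completes or if pain is unrelated to completion, and it changes sign if non-completers had less pain, so no direction is claimed. There is no hypothesis test (SAP 6.2) and no stated pain threshold, so no success criterion in the plan is affected. The benefit of changing it is a descriptive summary that covers the people it describes.

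**What to change.** Run Table 14.2.4 on the Safety population, including at each treatment visit every treated participant with a computable score, and change its label in SAP 15.1. In SAP 9.2.4, add one sentence making overall pain an exception to the Evaluable rule. The score definition in SAP 5.3 and the other exploratory summaries stay as they are.

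The cost is one population flag and one sentence; the data are already collected and listed. Because n may then differ between the two treatment visits, the two means may not cover the same participants. The n that SAP 6 already requires for continuous summaries will show this, and a footnote to the table can say so.
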